6.1 Risk assessment

6.1.1 Benefit/Risk Assessment

A Trial Risk Assessment has been completed to identify the potential hazards associated with the trial and to assess the likelihood of those hazards occurring and resulting in harm. This risk assessment has been completed in accordance with the MRC/DH/MHRA Joint project guidance document 'Risk-adapted approaches to the management of Clinical Trials of Investigational Medicinal Products' and includes:

- 1. The known and potential risks and benefits to human participants
- 2. How high the risk is compared to normal standard practice
- 3. How the risk will be minimised/managed

6.1.2 Risk assessment of AZD7442

The two monoclonal antibodies that make up AZD7442 both target SARS-CoV-2 spike protein for neutralization of the virus and do not have a human target. As such, the risks associated with AZD7442 are akin to risks associated with the administration of any immunoglobulin with no risk associated with mechanism of action.

As with other immunoglobulins, risks include but are not limited to, anaphylaxis and other serious hypersensitivity reactions including immune complex disease. Other risks include injection site reactions, and Antibody-dependent enhancement (ADE) disease, the latter of which is a theoretical risk.

Two different syndromes exist: 1) ADE, which involves increased binding efficiency of virus-antibody complexes to Fc receptor bearing cells and which triggers virus entry. The mAbs in AZD7442 have been designed with a modification to prevent binding to cellular Fc receptors, so the risk of ADE occurring via this mechanism should range from very low to none. 2) VAERD, which is a distinct clinical syndrome that occurred in young children in the 1960s when whole inactivated virus vaccines for measles and RSV were tested. Immunizing with limiting doses of RSV antigen, especially with conformationally incorrect antigens, can result in 2 major types of immunological phenomena: a) A relatively high ratio of antibody that binds, but does not neutralize, virus could potentially result in immunogenic cell death and complement activation (leading to inflammation and airway obstruction); b) immunization with whole inactivated virus vaccines can result in allergic inflammation characterized by, e.g., increased mucus production, airway hyperresponsiveness, and attenuated cytolytic T cell activity (T helper 2 cell immune response). This mechanism, induced by vaccines, should not be provoked by mAbs.

At present, there are no identified risks nor emerging safety profiles associated with AZD7442. The potential impact of the trial drug on other medicinal products including vaccines (including any SARS-CoV-2 vaccine) is not known. There is a possibility that receiving the trial drug prior to vaccination may result in the vaccine being less effective up to 9 months to 1 year or more or may cause a vaccine to have other currently unknown side effects.

No data are currently available to characterize the effects of giving AZD7442 to a person who has received a course of vaccination against SARS-CoV-2. Data from animal studies reported that prior AZD7442 administration did not alter either the cellular or the humoral immune responses elicited by subsequent SARS-CoV-2 vaccinations. Based on these results, AZD7442 is not anticipated to interfere with vaccine efficacy. More detailed information about the known and expected benefits and potential risks of AZD7442 can be found in the AZD7442 IB. There have been no events of anaphylaxis or other serious allergic reactions in the FTIH Phase I trial D8850C00001, D8850C00002 or D8850C00003 studies. There was one report of anaphylaxis: 1 (0.0%) participant in the AZD7442 group (classified as non-serious) in the PROVENT study.

6.1.3 Risk assessment of booster vaccines

Risk associated with the vaccine boosters also listed as IMPs within this trial are considered comparable to standard of care (Type A). It is not anticipated that the pre-dosing with AZD7442 would increase risks of the SARS-CoV-2 vaccines listed above.

6.1.4 Benefit Assessment

Recipients of AZD7442 do not have any guaranteed benefit. However, AZD7442 followed by SARS-CoV-2 vaccination may be efficacious and offer participants highly vulnerable to infection enhanced protection from SARS-CoV-2.

6.1.5 Overall Benefit: Risk Conclusion

Taking into account the measures taken to minimize risk to participants in this trial, the potential risks identified in association with AZD7442 and SARS-CoV-2 vaccination are justified by the anticipated benefits that may be afforded to participants at risk of SARS-CoV-2. This trial has been categorised as TYPE B, where the level of risk is somewhat higher than the risk of standard medical care. A copy of the trial risk assessment may be requested from the Trial Manager. The trial risk assessment is used to determine the intensity and focus of monitoring activity (see section 23).

7 Site and Investigator selection

This trial will be carried out at participating sites within the UK. All sites who are interested in participating in the trial will be required to complete a registration form to confirm that they have adequate resources and experience to conduct the trial.

Patients will be identified and recruited at the participating hospital sites. Each participating site will:

- 1. Identified a suitably qualified PI
- 2. Be provided with protocol specific training before being activated for recruitment
- 3. Be provided with a local document package in line with HRA guidance (see HRA website: www.hra.nhs.uk). For sites in England this package will be provided simultaneously to both the trial delivery team and the research management team. For sites in Scotland and Wales the package will be provided as required by the devolved administrations.
- 4. Be provided with copies of the REC, HRA and competent authority (CA) approvals for the trial. The approval process includes granting favourable opinion of the host care organisation/PI.

Before any Site can begin recruitment, the following documents must be in place and copies sent to [contact]

- 1. Confirmation of Capacity and Capability (C&C) from R&D department following sharing of local information pack.
- 2. Favourable opinion of host care organisation/PI from Main Ethics committee
- 3. A signed Trial Agreement including MTA
- 4. Current Curriculum Vitae and GCP training certificate of the Principal Investigator (PI)
- 5. Completed Site Delegation Log and Roles and Responsibilities document
- 6. Full contact details for all host care organisation personnel involved, indicating preferred contact
- 7. A copy of the most recent approved version of the Participant Information Sheet(s) and Consent Form(s), and Withdrawal of Consent Form on host care organisation headed paper
- 8. A copy of the most recent approved GP letter and invitation letter on host care organisation headed paper
- 9. A set of laboratory normal ranges and laboratory certification/accreditation from the host care organisation laboratory being used for analyses
- 10. Returned Source Data Agreement signed by the PI.
- 11. Pharmacy confirmation that they have received the first shipment of IMP prior to opening the site.
- 12. Pharmacy confirmation that they have boosters available at site.

Upon receipt of all the above documents, the Trial Manager will send written confirmation to the Principal Investigator/lead Research Nurse detailing that the centre is now ready to recruit participants into the trial. This letter/email must be filed in each site's Site File. Along with the written confirmation, the site should receive their trial drug supplies and a trial pack holding all the documents required to recruit into the Trial.

Occasionally during the trial, amendments may be made to the trial documentation listed above. CTR will issue the site with the latest version of the documents as soon as they become available. It is the responsibility of the CTR to ensure that they obtain local R&D approval for the new documents.

All documentation must be stored in the Investigator Site File (ISF) at the site and in the Trial Site File (TSF) at the CTR. The CTR must be notified of any changes to the trial personnel and their responsibilities during the running of the trial and the respective trial files must contain this up-to-date information.

Site initiation will be by teleconference.

8 Participant selection

Participants are eligible for the trial if they meet all of the following inclusion criteria and none of the exclusion criteria apply. All queries about participant eligibility should be directed to the Trial Manager before randomisation/registration.

Sites are encouraged to recruit a broad range of participant ethnic diversity and ages. Pls and sub-ls are encouraged to prioritise recruiting participants across a broad range of participant disease groups within each sub-cohort in order to obtain a reasonable breadth across each disease cohort. Recruitment into sub-groups will be regularly monitored by the trial team who may request that recruitment of particular disease sub-groups be paused. To support regular reporting of subgroup recruitment, we request that the baseline eCRFs and eligibility form is prioritised for data entry and that screening logs are updated regularly as per section 9.

8.1 Inclusion criteria

The participant must satisfy the following criteria to be eligible for the trial:

All participants

- 1. Provide written informed consent.
- 2. Previously completed SARS-CoV-2 vaccinations given as part of standard care at the time of enrolment.
- 3. Able and willing (in the Investigator's opinion) to comply with all trial requirements.
- 4. Willingness to practice continuous effective contraception during the first 3 months of the trial and, if appropriate, a negative pregnancy test on the day of screening.
- 5. Provide access to all medical records with respect to current and past medical treatments.
- 6. Have one or more of the following eligible conditions.

7. Adults ≥18 years

Eligible Conditions

Cohort 1: Haematological malignancies

Patients with a diagnosis of haematological malignancies and receiving one the following treatments:

- Cohort 1a Patients receiving active therapy with immunosuppressive or immunomodulating agents including:
 - B-cell targeted therapies (rituximab or other anti-B-cell Ab therapy) used either as monotherapy or in combination with cytotoxic therapy in lymphoma / chronic lymphoproliferative disorders

OR

• JAK inhibitors (ruxolitinib or equivalent) in myeloproliferative neoplasms (MPNs)

OR

• ImiD drugs (thalidomide, lenalidomide, pomalidomide or equivalent) in myeloma and other plasma cell dyscrasias

OR

• BTK inhibitors (ibrutinib or equivalent) in chronic lymphocytic leukaemia / chronic lymphoproliferative disorders

OR

- Treatment within 24 months with lymphodepleting agents followed by chimaeric antigen receptor (CAR) T-cell therapy for any haematological malignancy
- Cohort 1b Patients receiving aggressive therapy expected to cause temporary ablation of immune function including:
 - Acute leukaemia (AML or ALL) being treated with curative intent using intensive combination chemotherapy schedules (excluding acute promyelocytic leukaemia)

OR

• Patients within 24 months of receipt of allogeneic stem cell transplant or receiving systemic immunosuppression for graft versus host disease.

Cohort 2: Solid Tumours

• Early (Cohort 2a) or advanced cancer (Cohort 2b) (solid organ) undergoing systemic cancer treatment. Hormone treatments given alone such as tamoxifen or an aromatase inhibitor or LHRH agonist for early or advanced breast and prostate cancer are not considered to be a systemic treatment.

• Cancer patients are considered eligible for the trial if they have had a dose of systemic treatment within 42 days of trial entry.

Cohort 3: Renal/hepatic disorders

Cohort 3a - Renal Disorders:

Patients with kidney disease who fall into one of the following groups:

- Currently receiving immunosuppression
- Dialysis including in-centre and home haemodialysis, peritoneal dialysis
- Transplant recipient receiving immunosuppression

Cohort 3b - Hepatic disorders:

• Patients with liver cirrhosis, autoimmune liver disease and liver transplant.

Cohort 4: Inflammatory disorders

- Patients receiving T-cell co-stimulation modulators, B-cell targeted therapies (including rituximab), tumour necrosis factor inhibitors (TNFi), soluble TNF receptors, interleukin (IL)-6 receptor inhibitors, IL-17 inhibitors, IL 12/23 inhibitors, IL 23 inhibitors or JAK inhibitors
- Patients who had received any immunotherapies listed above in the previous 3 months for autoimmune diseases, except in the case of rituximab treatment within the previous 6-month period.
- Patients receiving or had received in the previous 6 months immunosuppressive chemotherapy
- Patients receiving systemic immunosuppression for a chronic inflammatory disorder.
- Cohort 4a will include participants receiving rituximab and cohort 4b will include participants receiving non-rituximab immunosuppressants

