- All AEs reported were mild in intensity, with the exception of the following events of moderate intensity: urinary tract infection (1 subject) in Cohort 1a; headache, malaise (1 subject each) and urinary tract infection (1 subject) in Cohort 1b; dysmenorrhea and headache (1 subject each) and toothache (2 participants) in Cohort 2; headache, back pain, and arthralgia (1 subject each) in Cohort 3; and back pain (1 subject) in Cohort 4.
- There were no haematology, clinical chemistry, or vital signs findings of concern in any subject.

In addition, by Day 211, no participants in the study tested positive for ADA to either AZD8895 or AZD1061. Since ADA-positive to AZD7442 is defined as having a positive result to AZD8895 and/or AZD1061, no participants tested positive for ADA to AZD7442. Thus, both ADA prevalence (percentage

ARDIF

of ADA-positive participants in the study) and ADA incidence (percentage of treatment-emergent ADApositive participants in the study) were 0%. The serum AZD8895 and AZD1061 concentrations observed in the Phase I study support that the PK of the 2 antibodies are similar. The half-life of AZD7442 is estimated to be ~ 90 days which will allow for long-term protection. Overall, the Cmax and AUC increased linearly with increasing IV dose. Administering AZD8895 and AZD1061 separately or together did not alter the PK of the mAbs as indicated by the overlapping serum drug concentrationtime curves. In addition, key exposure PK parameters such as AUC and Cmax for AZD8895 and AZD1061 were similar between the 2 dosing regimens.

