11.6 Permitted, Restricted, and Prohibited Medications

Permitted, restricted, and prohibited medications are summarized in Table 5. Any medication or vaccine (including over-the-counter or prescription medicines, vitamins, and/or herbal supplements) that the participant is receiving at the time of enrolment or receives during the trial must be recorded, along with:

- Reason for use
- Dates of administration, including start and end dates
- Dosage information, including dose and frequency

The Trial Physician should be contacted if there are any questions regarding concomitant or prior therapy

Use Category	Type of medication/treatment	Timeline/instructions
Permitted	Routine Vaccines	Licensed influenza vaccines are permitted at any time. All other routine non-COVID vaccines are permitted beginning > 30 days after IMP dose with the exception of patients receiving a haemopoietic stem cell transplant who may receive non-COVID vaccines at any time.
	Allergen immunotherapy	Allowed if participant has been receiving stable therapy for at least 30 days prior to Visit 1 and there is no anticipated change during the treatment period. Allergen immunotherapy should not be administered on the same day as IMP

Table 5: Permitted, restricted and prohibited medications

Centre for Trials Research Canolfan

	Commercial biologics,	Allowed, provided the
	prednisone,	participant is stable on
	immunosuppressive	maintenance dose (at steady
	medications (e.g., azathioprine,	state) prior to Visit 1, and must
	tacrolimus, cyclosporine,	not be administered on the
	methotrexate, or cytotoxic	same day as IMP
	chemotherapy,	
	immunotherapy or targeted	
	treatment for cancer)	
		tant medications prescribed by
		ospital team for management of nd/or for health maintenance.
		hospital providers, or where
		hould prescribe appropriate
		eatments deemed necessary to
		and comfort during the trial.
		-19 after receiving IMP should be
	treated according to local	standard of care, including
	investigational agents within a c	linical trial setting.
Prohibited	Not applicable	Not applicable
Restricted	Contraceptive methods	See section 14.8
	Blood/plasma donation	Participants must abstain from
		donating blood or plasma from
		the time of informed consent
		and for 5 half-lives after dose of
		study drug, i.e. one year.
	Standard of care COVID-19	Participants must not obtain
	vaccines	standard of care approved
		COVID-19 boosters until at
		least 3 months after receiving

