13.1 Assessments

Baseline Assessments

All baseline assessments should be performed after consent has been obtained and within 28 days of treatment. Participants will be required to attend clinic for blood sample collection and treatment. The following assessments will need to be done:

- Completion of eligibility checklist form
- Participant informed consent
- Full Medical History
- Randomisation as per Section 9.5 of the protocol
- Participants should be asked about their previous SARS-CoV-2 vaccination history. The information should be collected on the SARS-CoV-2 vaccine form.
- Prior and Concomitant Medications Review of any medications received within 28 days before the first dose of trial treatment
- Participant behavioural questionnaires (risk behaviour changes, PROMIS 10, EQ-5D-5L)

AZD7442 treatment (this can be done on the same day as baseline assessments)

Day 0

- A negative urine dipstick pregnancy test should be performed to confirm eligibility for women of child-bearing potential.
- Toxicity assessment (CTCAE 5.0)
- Blood sample collection and completion of the sample eCRF
- Safety bloods (full blood count (FBC), Urea and electrolytes (U&E), Liver function test (LFT) and bone profile)
- Full Physical Examination including vital signs, weight and height
- Blood sample collection prior to AZD7442 dosing and completion of the sample eCRF
- Routine (asymptomatic) lateral flow testing for SARS-CoV-2 infection (only subset of participants). If the lateral flow test is positive for SARS-CoV-2 infection, a nasal PCR swab should be taken to be sent for testing.

NB: The assessments above should be performed *before* the administration of AZD7442.

• Dosing with AZD7442

On Day 14 post AZD7442 (+/- 3 days):

• Toxicity assessment via telephone consultation with patient to check on symptoms.

On Day 28 post AZD7442 (+/- 3 days):

- Clinical review
- Vital signs
- Blood sample collection and completion of the sample eCRF
- Safety blood samples (FBC, U&E, LFT and bone profile)
- Concomitant Medications Review
- Toxicity assessment (CTCAE 5.0)
- Routine (asymptomatic) lateral flow testing for SARS-CoV-2 infection (only subset of participants). If the lateral flow test is positive for SARS-CoV-2 infection, a nasal PCR swab should be taken to be sent for testing.

NB: The assessments above should be performed *before* the administration of SARS-CoV-2 vaccine booster.

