14.8.2 Contraception

Women of Childbearing potential

AZD7442 in this trial has a demonstrated or suspected human teratogenicity/fetotoxicity. Women of childbearing potential who are sexually active must agree to use, with their non-sterilized male partner, an approved method of highly effective contraception from the time of AZD7442 administration until 3 months after. In instances where a WOCBP has a sterilized male partner, the vasectomized partner must have received a medical assessment of surgical success. Women should be stable on their chosen method of birth control for at least one month before dosing. Highly effective contraception is summarized in Table 11.

Table 11: Highly effective methods of contraception

Barrier method	Hormonal method	
 Intrauterine device Intrauterine hormone-releasing system (IUS)^a Bilateral tubal occlusion Vasectomized partner ^b Sexual abstinence ^c 	 Combined (oestrogen- and progestogen-containing hormonal contraception) associated with inhibition of ovulation Oral (combined pill) Intravaginal Injectable Transdermal (patch) Progestogen-only hormonal contraception associated with inhibition of ovulation Oral Injectable Transdermal (patch) 	

a This is also considered a hormonal method.

b Provided that partner is the sole sexual partner of the woman of childbearing potential study participant

and that the vasectomized partner has received medical assessment of the surgical success.

c Sexual abstinence is considered a highly effective method only if defined as refraining from heterosexual

intercourse during the entire period from the time of AZD7442 administration until 3 months after and if it is

the preferred and usual lifestyle of the participant.

Male Participants

To avoid transfer of fluids to a sexual partner, all male participants must use a condom starting from the time of AZD7442 administration until 3 months after. Contraception for female partners of childbearing potential may be considered, but is not required for this protocol.

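### Inclusion criterion 4 is looser than the contraception rule in section 14.8.2, and Table 5 equates five half-lives with one year against a stated half-life of about 90 days

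*Protocol*

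**What the plan says.** **Eligibility.** Criterion 4 in section 8.1 stands under the heading for all participants, men and women, and reads "Willingness to practice continuous effective contraception during the first 3 months of the trial". The synopsis uses the same words. Exclusion criterion 8, on planned pregnancy, counts its three months from AZD7442 administration.

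**Binding rule.** Section 11.6.1 obliges participants to follow section 14.8. For sexually active women of childbearing potential, 14.8.2 requires "an approved method of highly effective contraception from the time of AZD7442 administration until 3 months after", with the accepted methods in Table 11. It adds: "Women should be stable on their chosen method of birth control for at least one month before dosing". For men it says that "all male participants must use a condom starting from the time of AZD7442 administration until 3 months after".

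**Visit timing.** Section 13.1 allows baseline assessments up to 28 days before treatment, but also permits both on one day: "AZD7442 treatment (this can be done on the same day as baseline assessments".

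**Donation.** Table 5 in section 11.6 bars blood and plasma donation from consent "and for 5 half-lives after dose of" study drug, and gives this as one year. Section 4.6 states: "The half-life of AZD7442 is estimated to be ~ 90 days".

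**Risk statements.** Section 14.8.2 describes AZD7442 as having demonstrated or suspected harm to the human foetus. Section 6.1.2 says that the antibodies have no human target and that no risks have so far been identified.

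**The concern.** Section 8 makes a participant eligible when its criteria are met, and criterion 4 is the only inclusion criterion specific to contraception. If it is less demanding than the section that governs conduct, a site can follow section 8 correctly and still dose a woman who does not meet the protocol's own precaution. The result would be avoidable deviations in a participant-protection rule, with different sites reading the rule differently.

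The donation rule raises a separate question. It gives one restriction in two forms, a multiple of the half-life and a calendar duration, and the two disagree at the half-life that the protocol reports. A participant told one year and a participant told five half-lives would stop abstaining at different times.

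**Working it through.** **1. Criterion 4 beside section 14.8.2**

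| Element | Criterion 4 (8.1, synopsis) | 14.8.2, women of childbearing potential |
|---|---|---|
| Method level | *effective* | *highly effective*, methods listed in Table 11 |
| Clock starts | start of the trial, not defined | AZD7442 dosing |
| Prior use | none | about one month before dosing |

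**2. Size of the start-point difference**

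Inputs: the baseline-to-dosing gap is 0 to 28 days (section 13.1); three months is taken as 3 × 30.44 = 91.3 days.

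If the trial is taken to start at baseline, the criterion 4 period ends, in days after dosing, at 91.3 − gap:

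- gap 0 days: 91.3, shortfall against 14.8.2 of 0 days
- gap 14 days: 77.3, shortfall 14 days
- gap 28 days: 63.3, shortfall 28 days

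If the trial is taken to start at Day 0, the day of dosing, the shortfall is 0 in every case. The range is therefore 0 to 28 days.

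**3. Prior use**

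Same-day baseline and dosing removes the start-point gap but leaves no interval in which a woman who first agrees to contraception at baseline could build up prior use. If a month is read as 30 days, even the longest gap of 28 days is 2 days short for her. A woman already established on a method meets 14.8.2 whatever the gap. Neither the inclusion nor the exclusion list distinguishes these two women.

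**4. Donation window**

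Inputs: multiple of 5 and duration of one year (Table 5); half-life of about 90 days (section 4.6).

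- The plan's equality, 5 half-lives = 365 days, needs a half-life of 365 / 5 = 73 days.
- At 90 days: 5 × 90 = 450 days, and 450 − 365 = 85 days longer than stated.
- Conversely, 365 / 90 = 4.06 half-lives in one year.
- Because the half-life is given as approximate, take 80 to 100 days as an assumed range: 5 × 80 = 400 and 5 × 100 = 500 days. The equality fails throughout that range.

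The plan's figure is not reproduced.

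**The case against.** The strongest reply is that the binding rule already covers the gap. Section 11.6.1 imposes 14.8 on every participant, inclusion criterion 3 requires willingness to comply with all trial requirements, and exclusion 8 is anchored to dosing. This stands to the extent that criterion 4 does not end the 14.8.2 obligation. A reader might infer that contraceptive cover may stop about 63 days after dosing; the documents do not support that. But a general willingness to comply cannot supply a month of prior use that has not happened.

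The difference in method level is partly explained by scope. Criterion 4 covers men as well, for whom 14.8.2 asks only for a condom, which is not in Table 11, so a single phrase for both sexes could hardly say *highly effective*. The mismatch therefore concerns women. The prior-use sentence is also worded as *should*, next to a *must* for the method, so its force is itself unclear.

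A reader might also infer that the three-month contraception and gamete-donation windows are wrong because three months is about one half-life. The documents do not support that either. Those windows are given in months with no half-life basis, and the protocol sets no threshold for remaining drug. Only the blood and plasma rule is expressed in half-lives.

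On the risk statements, *suspected* in 14.8.2 and no *identified* risk in 6.1.2 are not strict opposites, so this is an unexplained tension and not a proven contradiction.

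Finally, section 13.1.1 records that recruitment was paused in April 2023. The eligibility point therefore matters for new participants only if recruitment resumes; the donation rule still concerns people already dosed.

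**Conclusion.** The concern holds in two limited parts.

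First, criterion 4 is looser than 14.8.2 for women of childbearing potential on method level and prior use and, depending on the reading, on start point by 0 to 28 days. The upper figure assumes that the trial starts at baseline and that baseline precedes dosing by the full 28 days. The prior-use gap does not depend on how the start of the trial is defined. The eligibility checklist is not among the documents, so whether it already carries the 14.8 items is unknown.

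Second, Table 5 and section 4.6 cannot both be right as written: about 450 days against 365 at a 90-day half-life, or 400 to 500 days over the assumed range. This is an arithmetic conflict, unrelated to contraception.

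Both are inconsistencies in participant-protection wording. They do not show that any participant was left without a contraception requirement, and they affect no estimate, test or sample size.

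**What to change.** 1. In section 8.1 and the synopsis, make criterion 4 refer to 14.8.2 separately for women of childbearing potential and for men, so that start point, method and prior use are checked before dosing. Alternatively, remove from 14.8.2 whatever is not intended. Either way, state whether prior use is mandatory.
2. In Table 5, reconcile the half-life multiple and the calendar duration with each other and with the half-life in section 4.6.
3. Reconcile the teratogenicity sentence in 14.8.2 with the risk description in 6.1.2.

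The clinical choice of rule, method and duration belongs to the sponsor; the passages need only agree.

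The cost is a few lines of protocol text and, if needed, a line in the eligibility checklist. If prior use becomes a check before dosing and recruitment resumes, a few women might be dosed later.
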